**• HCV infection**

The evolution of Hepatitis C (HCV) and the rate of progression of HCV related allograft fibrosis will be evaluated. The HCV viral load, the incidence of and response to HCV antiviral treatment and the incidence of de novo hepatocellular carcinoma (HCC) malignancies and the rate of recurrence of HCC will be assessed. Biopsies will be obtained in all patients who are listed as HCV positive by serology testing, at time of transplantation and at Month 12. The biopsies will be read by the local pathologist (who will remain blinded to patient treatment) according to the Ishak-Knodell scores (Ishak 1995) (see Appendix 9).

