## 7.6 Safety

### 7.6.1 Adverse events

An adverse event is the appearance or worsening of any undesirable sign, symptom, or medical condition occurring after start of study drug even if the event is not considered to be related to study drug. Medical conditions/diseases present before obtaining informed consent have to be documented as medical history and are only considered adverse events if they worsen after study start. Abnormal laboratory values or test results constitute adverse events only if they induce clinical signs or symptoms, require study drug discontinuation or require therapy.

The occurrence of adverse events should be sought by non-directive questioning of the patient at each visit during the study. Adverse events also may be detected when they are volunteered by the patient during or between visits or through physical examination, laboratory test, or other assessments. All adverse events must be recorded on the Adverse Events CRF with the following information:

1. the severity grade (mild, moderate, severe)
2. its relationship to the study drug (everolimus) and tacrolimus (suspected/not suspected)
3. its duration (start and end dates or if continuing at final exam)
4. whether it constitutes a serious adverse event (SAE)

An SAE is defined as an event which:

- is fatal or life-threatening
- results in persistent or significant disability/incapacity
- constitutes a congenital anomaly/birth defect
- requires inpatient hospitalization or prolongation of existing hospitalization, unless hospitalization is for:
  - routine treatment or monitoring of the studied indication, not associated with any deterioration in condition
  - elective or pre-planned treatment for a pre-existing condition that is unrelated to the indication under study and has not worsened since the start of study drug
  - treatment on an emergency outpatient basis for an event not fulfilling any of the definitions of a SAE given above and not resulting in hospital admission
  - social reasons and respite care in the absence of any deterioration in the patient's general condition
  - treatment of acute rejection; acute rejections are considered to be a protocol exempted event. They should not be reported simply because they result in a hospitalization and thus meet the criteria for an SAE. Acute rejections should be reported as SAEs only if they are unusual in appearance, clinical course and/or are graft threatening

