#### **Adverse events/infections**

Data collected by AE CRFs and by Infection CRFs will be coded using MedDRA. The number of AE/patients with AE will be summarized by MedDRA system organ class and preferred term. Additionally, AE will be summarized by maximum severity, and for AE with suspected drug relation, serious AE (SAE), and AE leading to permanent discontinuation of study drug. In addition to being analyzed together with AE data, the incidence of bacterial, viral and fungal infections will be tabulated separately for all infections, by maximum severity, for infections with suspected drug relation, serious infections and infections leading to premature discontinuation of study drug. These summary tables will include adverse events of special interest, such as New Onset of Diabetes Mellitus (NODM, for definition see [Section 7.6.4](#)), *de novo* HCC malignancies, HCV- and HCC-related fibrosis.

All information pertaining to AE noted during the study will be listed by treatment group and patient, detailing the verbatim term given by the investigator, MedDRA preferred term and system organ class, start/end dates, severity, seriousness, relationship to study drug and action taken. The AE onset will also be shown relative (in number of days) to the date of initial dose.

AE starting before, or 28 or more days after the discontinuation of study medication, will not be considered as treatment-emergent and will not be included in AE/infection summary tables but listed only.

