- To evaluate the incidence of and time to renal replacement therapy as concomitant therapy of special interest.

Safety related secondary objectives were

- To evaluate the incidence of Adverse Events (AEs)/Infections/Serious Adverse Events (SAEs).
- To evaluate the incidence of treatment-related side effects, including incidence of new onset diabetes mellitus (NODM), evolution of metabolic parameters as subdivisions of serum/plasma lipid panel, neurotoxicity and hypertension.
- To evaluate the incidence and reason (e.g. AE) of premature discontinuation of study medication and premature discontinuation from the study.
- To evaluate the incidence and reason (e.g. AE) of interruption and dose adjustment of study medication.

Virus (HCV, CMV) and Hepatocellular Carcinoma (HCC) related secondary objectives were

- To evaluate the incidence of HCV and HCV related fibrosis.
- To evaluate HCV viral load (HCV- messenger ribonucleic acid (mRNA) levels overall and by genotype).
- To evaluate incidence of and response to HCV antiviral treatment.

- To evaluate the rate of recurrence of HCC at 12 post-transplantation in patients with a diagnosis of HCC at the time of liver transplantation adjusting for various risk factors, such as number of tumor nodules, total tumor size and tumor metastasis.
- To evaluate the incidence of de novo HCC malignancies. (adverse event of special interest)
- • Incidence and severity of CMV viral infections.

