### **2.6.1.1 Adverse events of special interest / grouping of AEs**

Adverse of special interest were

- New onset of diabetes mellitus,
- de novo HCC malignancies,
- HCV- and HCV-related fibrosis
- Proteinuria
- CMV viral infections

For the subgroup of patients with HbA1c baseline range of 5.7 to 6.4%, the onset of diabetes will be calculated additional.

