**Changes in statistical methods in comparison to the protocol:**

The Virus (HCV, CMV) and Hepatocellular Carcinoma (HCC) related secondary objective “• To evaluate rates of progression of HCV related allograft fibrosis are deleted. Reason is, that the in case from HCV the biopsies were not performed adequately.

The incidence of proteinuria of  $0.5 - <1.0$  g/day,  $1.0 - <3.0$  g/day and  $\geq 3.0$  g/day could not be analysed, because in urine analysis protein is measured in g/l and not in g/day. Therefore, proteinuria could be only documented as adverse event. Therefore proteinuria is defined as further adverse event of special interest.

CNV viral infection were defined as further adverse event of special interest.

Treatment emergent events were defined as all adverse started at baseline or later.

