### **Efficacy-related objectives**

For the efficacy related events only the events between Visit 2 (Baseline) and Day 360 are relevant. That means, that all events outside before Baseline and after 360 are excluded from this analysis.

**Death:** All Cases documented on the following pages

- End of treatment
- Study completion

Date of event = Date of Death – Date of Baseline + 1

**Graft loss:** All cases documented on page Graft Loss

Date of event = Date of Graft loss – Date of Baseline + 1

**Acute rejection:** All rejections documented on page Liver Allograft Rejection with final clinical diagnosis “Acute rejection diagnosed by biopsy”, “Acute rejection diagnosed without biopsy” or “Acute and chronic rejection”.

Date of event = Date rejection was first suspected – Date of Baseline + 1

**Treated acute rejection:** All rejections documented on page Liver Allograft Rejection with [final clinical diagnosis “Acute rejection diagnosed by biopsy”, “Acute rejection diagnosed without biopsy” or “Acute and chronic rejection”] and anti-rejection therapy.

Date of event = Date rejection was first suspected – Date of Baseline + 1

**Biopsy proven acute rejection:** All rejections documented on page Liver Allograft Rejection with final clinical diagnosis “Acute rejection diagnosed by biopsy”.

Date of event = Date rejection was first suspected – Date of Baseline + 1

**Treated Biopsy proven acute rejection:** All rejections documented on page Liver Allograft Rejection with final clinical diagnosis “Acute rejection diagnosed by biopsy and anti-rejection therapy”.

Date of event = Date rejection was first suspected – Date of Baseline + 1

For **Kaplan-Meier analysis** the first occurred event will be used. If no event is treated the time will be censored at min (day of visit Month 12, 360). If visit Month was not performed, the last visit until Month 12 will be used.

Day of vist = Visit Date – Date of Baseline + 1

**Adverse of special interest** were defined as followed:

AE of special interest	Identification
HCV (Hepatitis C Virus)	PT „HEPATITIS C“ OR “HEPATITIS C VIRUS TEST POSITIVE” OR “CHRONIC HEPATITIS C” OR “ACUTE HEPATITIS C” OR “HEPATITIS C ANTIBODY” “HEPATITIS C ANTIBODY POSITIVE” “HEPATITIS C CORE ANTIBODY POSITIVE” PT contains “HEPATITIS C RNA” “HEPATITIS C VIRUS TEST” “HEPATITIS C VIRUS TEST POSITIVE”
HCV related fibrosis	PT “HEPATIC FIBROSIS” (Query: HCV related?)
CMV	HLT “CYTOMEGALOVIRAL INFECTIONS”
Proteinuria	SMQ “PROTEINURIA”

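### HCV-related fibrosis is still listed as an incidence objective but is counted only from an adverse event term, which probably understates it by an unknown amount

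*SAP*

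**What the plan says.** SAP 1.3 lists among the secondary objectives: "To evaluate the incidence of HCV and HCV related fibrosis". SAP 2.6.1.1 classes "HCV- and HCV-related fibrosis" as an adverse event of special interest. The table under SAP 5.5.2 gives the only working definition, "PT “HEPATIC FIBROSIS” (Query: HCV related". No section of the SAP analyses a biopsy stage for fibrosis.

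The protocol measures fibrosis by another route. Section 7.5 (HCV infection) states: "Biopsies will be obtained in all patients who are listed as HCV positive by serology testing, at time of transplantation and at Month 12". These are read by a local pathologist who is blinded to treatment, "according to the Ishak-Knodell scores", and Appendix 9 gives the staging scale.

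Two further protocol passages matter. Section 7.6.1 says: "Abnormal laboratory values or test results constitute adverse events only if they induce clinical signs or symptoms, require study drug discontinuation or require therapy". Section 10.5.2 (Adverse events/infections) names "HCC malignancies, HCV- and HCC-related fibrosis" among the events of special interest in the adverse event tables.

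SAP Section 4 deletes the objective on rates of progression of HCV-related allograft fibrosis: "Reason is, that the in case from HCV the biopsies were not performed adequately". It says nothing about what this means for the incidence objective, which stays.

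**The concern.** Fibrosis is a histological finding, and the protocol schedules biopsies in HCV-positive patients in order to see it. The adverse event form is not built to record every such finding. A count of the coded term is therefore a count of fibrosis that an investigator chose to report, or had to report, as an event. That is not the quantity the objective names.

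The background section of the protocol gives a possible effect on fibrosis in HCV-positive recipients as part of the reason for studying everolimus. A table with few events in both arms could be read as little fibrosis and no difference, when it would mainly reflect the data source. The source also moves from a blinded pathologist to investigators in an open-label trial, so reporting could differ by arm in either direction.

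**Working it through.** The documents give no expected fibrosis rate, no capture rate and no power for this objective, so there is no planned figure to reproduce. The check is first a comparison of passages, then an illustration under stated assumptions.

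**Passages side by side**

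1. *Instrument.* Protocol 7.5 uses biopsy at transplantation and Month 12. SAP 5.5.2 uses one MedDRA preferred term.
2. *Filter.* Under protocol 7.6.1 a test result becomes an adverse event by three routes: symptoms, stopping study drug, or treatment. Fibrosis found on a scheduled biopsy with none of these need not be reported. The scheduled post-transplant biopsy falls at Month 12, when study treatment ends, so for a finding first made there the drug-stopping route is essentially closed.
3. *Denominator.* SAP 2.6.1 reports numbers and percentages of patients per treatment group. It sets no HCV-positive denominator for this item, although SAP 5.5.1 already defines HCV class.
4. *Attribution.* The query on HCV relation has no rule saying who answers it or on what evidence.
5. *Consistency.* Section 4 removes progression because of inadequate biopsies. Incidence is kept, without explanation, on a source that does not measure stage.

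**Illustration**

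Inputs:
- 165 patients per arm (protocol 10.7).
- HCV-positive share 20 to 50% (assumption; the protocol background says only that the group is at least half of liver recipients in many countries). This gives m = 165 × 0.20 = 33 to 165 × 0.50 ≈ 82 per arm.
- True 12-month fibrosis p = 30 to 70% of HCV-positive patients (assumption).
- Capture c = share of true cases that become a coded event (assumption, varied).

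True cases per arm = m × p: 33 × 0.30 = 9.9 to 82 × 0.70 = 57.4.

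Reported cases per arm = m × p × c. Chance of no reported case in an arm = (1 − p × c)^m.

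| c | Reported cases per arm | Chance of none in an arm |
|---|---|---|
| 2% | 0.2 to 1.1 | 31 to 82% |
| 5% | 0.5 to 2.9 | 5 to 61% |
| 10% | 1.0 to 5.7 | 0.3 to 37% |
| 25% | 2.5 to about 14 | below 8% |
| 50% | 5.0 to 28.7 | 0.5% or less |

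The denominator adds a separate distortion. With m = 58 (35% of 165), p = 50% and c = 10%, the 2.9 reported cases are 5.0% of HCV-positive patients but 2.9/165 = 1.8% of the arm.

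A contrast between arms shrinks as well. An assumed true 50% versus 30% becomes 12.5% versus 7.5% at c = 25%, and 5% versus 3% at c = 10%. Approximate two-sided 5% power, for 33 to 82 HCV-positive patients per arm, falls from 38–75% with full histology to 10–19% and 6–10%. No test of this item is planned; the figures only show how little a null contrast would say.

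**The case against.** The strongest reply is that the adverse event route was not invented in the SAP. Protocol 10.5.2 already sends fibrosis to the adverse event tables, and protocol Section 10 contains no analysis of the Ishak-Knodell score. That stands: the inconsistency lies inside the protocol, and the SAP follows one side of it. (Protocol 10.5.2 prints HCC where the SAP prints HCV in naming the fibrosis; SAP Section 4 does not mention this difference.) It does not remove the problem, because the objective still names an incidence that the chosen source cannot be relied on to measure.

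A reader might infer that the adverse event rule shuts histology out altogether. It does not. The rule is conditional, a diagnosed condition can be reported as an event, and protocol 6.6.5 allows HCV treatment only on histological evidence of recurrent disease, so some biopsy findings meet the treatment route. Such cases may, however, be coded as hepatitis C, which has its own row in SAP 5.5.2.

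It is also fair that a biopsy analysis would be weak. The SAP calls the HCV biopsies inadequate, the control biopsy is not among the mandatory Month 12 items after early drug discontinuation (protocol Section 7, Visit 9), and the documents do not show that an Ishak stage was entered on a CRF. A single Month 12 biopsy also gives prevalence rather than incidence. These limits shape the fix. They do not support keeping the objective unchanged.

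**Conclusion.** The point holds in limited form. The retained incidence objective rests on adverse-event-reported hepatic fibrosis, which misses biopsy-detected fibrosis without symptoms, drug discontinuation or treatment. Incidence is likely understated, by an amount the documents do not allow anyone to compute.

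A reader might go further and expect a count near zero in both arms. That is not shown: under the assumptions above it needs capture of roughly 5 to 10% or less, and no capture rate is given. At 25 or 50% capture, cases would usually appear, though still with three quarters or half of them missing.

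The consequence is confined to one secondary objective with no confirmatory test. The eGFR analysis is untouched. What changes is whether the trial may say anything about fibrosis incidence; on the present definition it may not.

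**What to change.** Amend SAP 2.6.1.1, 5.5.2 and Section 4.

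1. Check whether the Ishak stage was captured. If so, describe it at Month 12 in HCV-positive patients (SAP 5.5.1 class) with a readable biopsy. Call it prevalence at Month 12, or increase in stage where an intraoperative biopsy exists. Give numbers biopsied and missing by arm. Judge adequacy separately from progression: Month 12 stage needs one biopsy, progression needs two.
2. If too few biopsies exist, drop the incidence objective in Section 4 alongside progression, for the same stated reason.
3. In either case, report the coded term only as hepatic fibrosis reported as an adverse event. Use HCV-positive patients as denominator, state the rule that settles the HCV-relation query, and draw no conclusion on fibrosis incidence.
4. Note in Section 4 that protocol 7.5 and 10.5.2 point to different sources, and say which one the analysis uses.

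The cost is SAP wording and at most one descriptive table, provided the stage was recorded. The downside of the biopsy table is a small denominator and selection by biopsy availability, which is why the missing numbers must be shown.

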### **Virus (HCV, CMV) and Hepatocellular Carcinoma (HCC) related objectives**

- To evaluate the incidence of HCV and HCV related fibrosis.
- To evaluate rates of progression of HCV related allograft fibrosis.
- To evaluate HCV viral load (HCV- messenger ribonucleic acid (mRNA) levels overall and by genotype).
- To evaluate incidence of and response to HCV antiviral treatment.
- To evaluate the rate of recurrence of HCC at 12 post-transplantation in patients with a diagnosis of HCC at the time of liver transplantation adjusting for various risk factors, such as number of tumor nodules, total tumor diameter, alpha fetoprotein level, etc.
- To evaluate the incidence of de novo HCC malignancies.
- Incidence and severity of CMV viral infections.

[figure not shown]

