### **Infections**

All infection episodes must be recorded on the Infection CRF; they should not be collected on the AE CRF. Infections should be listed with severity, relationship, sample site, genus and species of microorganism specified, start and end dates, action taken.

**CMV infection:** Information will be captured on laboratory-defined CMV (antigenemia-positive, PCR positive), CMV syndrome (fever for the last 2 days, neutropenia, leukopenia, viral syndrome) and CMV-disease (organ involvement), on the CMV-specific CRF. CMV and HCV viral load (HCV positive patients only) will be measured locally at baseline, month 1, 3, 6, 12, for evaluation of incidence and severity. Suspected CMV infections will be recorded on the Infection CRF and on the CMV-specific CRF-field during visits. CMV infections will be also assessed by donor/recipient constellation (D+R+ / D-R- / D+R- / D-R+).

**HCV infection:** HCV information will be recorded on the Infection CRF. HCV viral load (HCV positive patients only) will be measured locally at baseline, month 1, 3, 6, 12, for evaluation of incidence and severity. HCV genotype will be assessed locally at baseline (HCV positive patients only).

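### The SAP identifies CMV by a single MedDRA term group and leaves out the CMV-specific CRF grading and the donor/recipient breakdown that the protocol sets out, without saying so

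*SAP*

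**What the plan says.** Protocol 3.2 lists "Incidence and severity of CMV viral infections" among the virus-related secondary objectives, and SAP 1.3 keeps that objective.

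Protocol 7.6.1, under Infections, says how CMV is recorded: "Information will be captured on laboratory-defined CMV (antigenemia-positive, PCR positive), CMV syndrome", followed by "CMV-disease (organ involvement), on the CMV-specific CRF". It schedules local viral load measurements to evaluate incidence and severity. It also requires that "Suspected CMV infections will be recorded on the Infection CRF and on the CMV-specific CRF-field during visits", and it states that "CMV infections will be also assessed by donor/recipient constellation". Protocol 7.3 collects CMV serology for donor and recipient, and Appendix 7 defines CMV syndrome and organ disease.

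SAP 2.6.1 names the AE and Infection CRFs as the sources coded in MedDRA. SAP 2.6.1.1 makes CMV an adverse event of special interest. The identification table in SAP 5.5.2 gives one rule for it, the high-level term "CYTOMEGALOVIRAL INFECTIONS". SAP section 4 reports that CMV (mistyped as CNV) was made an event of special interest and says no more about it.

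**The concern.** The protocol built a specific instrument for this objective, and the SAP does not use it. A patient with asymptomatic viraemia and a patient with organ involvement would both count as one coded event, separated only by the investigator's general severity grade. The syndrome/disease distinction, which is what makes CMV severity interpretable, would not be reported. Neither would the split by donor/recipient serostatus.

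There is also a question of completeness. If a positive PCR or antigen result is recorded on the CMV-specific form but not on the Infection CRF, the SAP gives it no stated route into the CMV count. The trial is open-label, so a count that depends on whether an investigator reports an infection is a less secure basis for comparing arms than one that also uses scheduled laboratory results.

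**Working it through.** No arithmetic applies, because the documents give no CMV event rates or category counts. The check sets what the protocol collects against what the SAP analyses.

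1. **Objective.** It is the same in protocol 3.2 and SAP 1.3, and it covers both incidence and severity. It was not withdrawn.

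2. **Three-category classification.** Protocol 7.6.1 places it on the CMV-specific CRF. SAP 2.6.1 names only the AE and Infection CRFs as coded sources. No SAP section names the CMV-specific CRF or tabulates its categories.

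3. **Donor/recipient assessment.** Protocol 7.6.1 states it, and protocol 7.3 collects the serology. It appears neither in the SAP's subgroup list (1.3.1) nor in its safety section (2.6).

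4. **General severity.** Protocol 7.6.1 requires that "Infections should be listed with severity, relationship, sample site, genus and species of microorganism specified", so the Infection CRF carries a severity grade. SAP 2.6.1 tabulates infections, viral ones included, by maximum severity. This part of the objective is covered, although no CMV-only severity table is named.

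5. **Laboratory results.** Protocol 7.6.4 lists CMV, including pp65 antigen, among the laboratory variables. SAP 2.6.3 promises by-visit descriptive statistics for all laboratory variables, so a by-visit antigen summary may exist. It would not give the number of patients who ever had laboratory-defined CMV, nor their worst category. HCV viral load has its own summary (SAP 2.10), and CMV viral load has none named.

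6. **Route of a laboratory-only case into the count.** Under the AE definition, "Abnormal laboratory values or test results constitute adverse events only if they induce clinical signs or symptoms, require study drug discontinuation or require therapy". Infections, however, go on a separate form, and protocol 7.6.1 requires every infection episode to be entered there. If sites treated each positive PCR or antigen result as an infection episode, it would reach the coded data. If they entered it on the CMV form alone, it would not. With L patients having laboratory-defined CMV and a fraction f of them lacking an Infection CRF entry, f × L patients would be missed. Neither L nor f is given, and f could be zero.

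7. **Disclosure.** SAP section 4 gives reasons for dropping the HCV fibrosis progression objective and for changing the proteinuria analysis. For CMV it records only the special-interest status. The unused categories and the missing donor/recipient assessment are not mentioned.

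**The case against.** The strongest reply is that the SAP follows the protocol's own analysis section. Protocol 10.5.2 analyses infections from MedDRA-coded AE and Infection CRFs and promises no table from the CMV-specific CRF; section 7.6.1 concerns data collection. The SAP also goes further than protocol 10.5.2 by making CMV an event of special interest. This is fair, but 7.6.1 also says how CMV is to be assessed, and the retained objective needs an analysis that matches it.

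A reader might infer that severity is lost altogether. The documents do not support that: the Infection CRF grades severity and SAP 2.6.1 tabulates it.

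A reader might also infer that laboratory CMV is undercounted. That is not shown. All infection episodes belong on the Infection CRF, and suspected CMV goes on both forms. What the high-level term covers depends on MedDRA 20.0, which is not among the documents. The HCV rule in the same SAP table lists test-positive and RNA terms, but those are preferred terms and the CMV rule is a term group, so the contrast does not settle the matter.

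Two further points stand. The CMV-specific form is also completed by unblinded investigators and relies on local testing, so it is not free of ascertainment bias. And table shells exist outside the SAP (RAP Module 6, cited in the note to file), so a CMV table could exist without being named here. That does not remove the gap in the SAP as the governing plan.

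**Conclusion.** The point holds as a gap in the analysis plan. The SAP's only CMV-specific rule is one MedDRA term group. The three-category grading and the donor/recipient assessment from protocol 7.6.1 have no planned analysis, and SAP section 4 does not disclose this. Loss of laboratory-defined CMV is a possibility that depends on how sites completed the two forms. Its size cannot be determined from the documents, and no percentage should be attached to it.

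The consequence is modest. CMV is outside the single confirmatory hypothesis, and the primary endpoint, sample size and type I error are unaffected. The conclusion assumes that the CMV-specific CRF was completed as the protocol requires.

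**What to change.** In SAP 2.6.1.1 and 5.5.2, define CMV incidence and severity from the CMV-specific CRF. Take the worst category per patient, ordered laboratory-defined CMV, CMV syndrome, CMV disease, and tabulate it by arm and by the four donor/recipient combinations. Keep the table based on the high-level term as supportive. Reconcile the two sources by reporting how many patients appear in one and not in the other, which would also show whether laboratory-only cases are being missed.

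Record the change in SAP section 4. If the CMV-specific CRF data cannot be used, state there that the grading and the donor/recipient assessment were dropped, and why.

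The cost is one or two descriptive tables from data the protocol already requires to be collected.

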### **New onset diabetes mellitus (NODM)**

The incidence of NODM will be assessed from Day 30 post-transplantation. NODM post-transplantation, in patients without diabetic history, is defined by any of the following:

- Two consecutive fasting plasma glucose levels  $\geq 126$  mg/dL (7.0 mmol/L) post-transplantation ( $> 30$  days).
- HbA1c  $\geq 6.5$  % from Day 75 onward.
- Diabetes mellitus (DM) reported as an adverse event that is prevalent after Day 30.
- Any concomitant medication with ATC level 2 code “A10” drugs used in diabetes, if prevalent after Day 30 and used for more than 30 days.

Non-diabetic patients, identified at the time of transplantation by all the following:

- DM or diabetic related terms were not included in medical history.
- Glucose (random)  $< 11$  mmol/L at the time of transplantation.
- HbA1c  $< 6.5$  % at the time of transplantation.

In addition, incidence of patients that are pre-diabetic will be assessed using an HbA1c range of 5.7 to 6.4%.

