### **2.6.3 Laboratory data**

Abnormalities according notable criteria (see Appendix 2 of the study protocol) were identified. The proportions of patients with clinically notable abnormalities according to the notable criteria were summarized. Descriptive statistics of absolute values as well as change from baseline of all laboratory variables were presented by visit and treatment group. A by-

patient listing of all clinically notable abnormal laboratory data was generated. Only assessments obtained up to 28 days after the discontinuation of study medication will be considered “on-treatment” and analyzed with relationship to immunosuppressive therapy.

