New onset diabetes mellitus	PT contains “Diabetes Mellitus” as Adverse event, but no PT containing “Diabetes Mellitus” as medical history
Hepatocellular Carcinoma (HCC)	HLT “HEPATIC NEOPLASMS MALIGNANT” OR “HEPATOBILIARY NEOPLASMS MALIGNANT UNSPECIFIED”
De novo HCC malignancies	HLT “HEPATIC NEOPLASMS MALIGNANT” OR “HEPATOBILIARY NEOPLASMS MALIGNANT UNSPECIFIED” as adverse event, but no HLT “HEPATIC NEOPLASMS MALIGNANT” OR “HEPATOBILIARY NEOPLASMS MALIGNANT UNSPECIFIED” as medical history

**Concomitant therapy of special interest** were defined as followed.

Concomitant therapy of special interest	Identification
Renal replacement therapy	PT „NON-DRUG THERPY: DIALYSIS“ or ATC CODE “B05Z (HEMODIALYTICS AND HEMOFILTRATES”

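### The SAP counts new-onset diabetes only from adverse event terms, dropping the protocol's glucose, HbA1c, medication and Day-30 rules without listing the change

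*SAP*

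**What the plan says.** Protocol 7.6.4 assesses NODM from Day 30 after transplantation and states: "NODM post-transplantation, in patients without diabetic history, is defined by any of the following". The four alternatives are:

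- a glucose criterion: two fasting values in a row at or above 126 mg/dL, later than 30 days;
- an HbA1c criterion: 6.5% or more, from Day 75;
- an adverse event criterion: "Diabetes mellitus (DM) reported as an adverse event that is prevalent after Day 30";
- a medication criterion: an ATC A10 drug, "if prevalent after Day 30 and used for more than 30 days".

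Non-diabetic status at transplantation needs three conditions together: no diabetes-related term in the history, random glucose below 11 mmol/L, and HbA1c below 6.5%.

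Protocol 10.5.2 carries this into the analysis. Its adverse event tables are to include "New Onset of Diabetes Mellitus (NODM, for definition see" Section 7.6.4.

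SAP 1.3 keeps the objective, "including incidence of new onset diabetes mellitus (NODM), evolution of metabolic parameters". The table of adverse events of special interest in SAP 5.5.2 then identifies a case by a preferred term containing diabetes mellitus, recorded "as Adverse event, but no PT containing" the same words in medical history. The row has no laboratory, medication or Day-30 element. The list of changed statistical methods in SAP Section 4 has four entries (progression of HCV fibrosis, proteinuria, CMV infection, and the definition of treatment-emergent events). NODM is not among them.

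**The concern.** The protocol's definition combines laboratory, medication and adverse event data so that a case does not depend only on an investigator choosing to report diabetes. The SAP rule depends on exactly that, in an open-label trial, and on which preferred term the report is coded to. A reader who sees NODM incidence kept as an objective, and no entry in Section 4, will assume that the protocol's definition was applied. What is at stake is the meaning of one reported safety rate in each arm.

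**Working it through.** The plan states no NODM rate or power figure, so there is nothing to reproduce. The check sets the two rules side by side.

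**1. What is kept.** Of the four outcome criteria, the SAP keeps one (the adverse event), without its Day-30 condition. Of the three baseline conditions it keeps one (history), and in narrower form: the protocol also rules out diabetes-related terms, while the SAP looks only for diabetes mellitus.

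**2. How patients are classified** (all otherwise non-diabetic at transplantation):

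| Patient | Protocol 7.6.4 | SAP 5.5.2 |
|---|---|---|
| Diabetes adverse event still present after Day 30 | NODM | counted |
| Meets the glucose criterion only, no diabetes adverse event | NODM | missed |
| Meets the HbA1c criterion only, no diabetes adverse event | NODM | missed |
| Meets the A10 criterion; adverse event unreported or coded to another term | NODM | missed |
| Diabetes adverse event starts after Visit 2, resolves before Day 30, no other criterion | not NODM | counted |

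**3. Why rows 2 and 3 can occur.** Under Protocol 7.6.1 an abnormal laboratory value is an adverse event only if it causes signs or symptoms, leads to stopping study drug, or needs therapy. A patient with qualifying values and none of these need not have an adverse event.

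**4. Why row 5 can occur.** SAP 2.6.1 counts events from baseline. Visit 2 falls on Day 7 to 21 after transplantation, so the window before Day 30 is 30 − 21 = 9 days to 30 − 7 = 23 days. The protocol counts a diabetes event from that window only if it persists beyond Day 30.

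**5. Whether another part of the SAP restores the definition.**
- SAP 2.6.1.1: "For the subgroup of patients with HbA1c baseline range of 5.7 to 6.4%, the onset of diabetes will be calculated additional". This uses HbA1c to define a baseline subgroup, not an outcome.
- SAP 2.6.3: "Descriptive statistics of absolute values as well as change from baseline of all laboratory variables were presented by visit and treatment group". Means by visit do not give the number of patients who meet a criterion.
- The notable-value summaries use Protocol Appendix 2, whose upper glucose limit is 250 mg/dL, not two values of 126 mg/dL, and which has no HbA1c limit.
- The treatment-emergent entry in SAP Section 4 changes when events begin to count. It does not disclose the loss of the Day-30 condition or of the other three criteria.

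**6. Whether the data are scheduled.** Fasting glucose and HbA1c belong to the blood chemistry taken at every visit from Visit 2 (Protocol 7.6.4 and Table 2). With Visit 2 as early as Day 7 and the visit windows of Protocol Section 7, the earliest Month 1 visit is Day 7 + 29 − 3 = 33, and the earliest Month 3 visit is Day 7 + 89 − 14 = 82. Five scheduled glucose values (Months 1, 3, 6, 9, 12) therefore fall after Day 30, and four HbA1c values (Months 3, 6, 9, 12) after Day 75. Patients who stop study drug are scheduled only for Visits 9a and 9 after that.

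**7. Minor point, proteinuria.** SAP Section 4 drops the three g/day categories because urine protein is reported in g/l. Concentration alone indeed cannot give a daily amount: at an assumed 1 to 3 L/day, 0.5 g/L is 0.5 to 1.5 g/day. But Protocol 7.5 measures proteinuria by a spot protein/creatinine ratio and 7.6.4 lists both urine variables. In the ratio the volume cancels: 0.5 g/L protein over 0.5, 1.0 or 2.0 g/L creatinine gives 1.0, 0.5 or 0.25 g/g. Protocol 10.5.1 plans a summary of this ratio by visit, and SAP 1.3 keeps it as an objective, yet for proteinuria SAP 2.5.2 describes only an adverse event table.

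**The case against.** The strongest reply is that diabetes in a closely followed transplant population will be reported as an adverse event anyway. Part of this stands. Protocol 7.6.1 lets an investigator report diabetes as a medical condition, and an abnormal value that needs therapy is already an adverse event. So it would be wrong to infer that every A10-treated patient is missed; the loss is confined to events not reported or coded to a term without diabetes mellitus. Patients who meet only a laboratory criterion and are untreated remain exposed.

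The missing glucose and HbA1c baseline conditions are also not wholly the SAP's doing. No chemistry is scheduled at screening (Protocol Table 2; Amendment 1, as described in SAP Section 4, moved it to baseline), so those conditions could often not be checked. The SAP should have said so.

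The protocol does not say how its two consecutive glucose values work when scheduled visits after Month 1 are 60 to 90 days apart. Applying the definition needs a stated rule, but this does not justify dropping the criterion.

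On proteinuria, a reader might infer an undisclosed change or categories that could simply be restored. The documents support neither. The change is listed with a reason, SAP 2.6.3 still summarizes laboratory variables by visit, and no factor for converting the ratio to g/day is given. An eligibility criterion in Protocol 5.1 treats the ratio as indicating daily excretion, but without a formula.

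**Conclusion.** The NODM rule in SAP 5.5.2 contradicts the definition that the protocol applies to the same tables, and the change is not listed. It keeps 1 of 4 criteria, without that criterion's Day-30 condition.

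A reader might infer that NODM is understated, or that the comparison between arms is biased in a known direction. The documents do not support this. Some cases are missed and some early, resolved events are added; no rates are given, and the net effect in either arm is unknown. Nor is there a planned confirmatory test of NODM whose power could be said to suffer. This is a descriptive secondary safety objective, and the primary eGFR analysis is unaffected.

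The conclusion rests on the text alone. How complete the glucose, HbA1c and urine creatinine data are cannot be seen. The proteinuria point is a clarification: the stated reason does not explain why the ratio is not used.

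**What to change.** 1. Replace the NODM row in SAP 5.5.2 with the four criteria of Protocol 7.6.4 and their Day-30 and Day-75 windows, derived from collected fasting glucose, HbA1c, ATC-coded medication and adverse event data.
2. Take non-diabetic status from medical history dated on or before transplantation, plus any glucose or HbA1c available then. The diagnosis date is collected (Protocol 7.2) and is needed because history is recorded up to randomization. State that no chemistry is scheduled at screening.
3. Report by arm how many patients are evaluable for each laboratory criterion.
4. Keep the adverse event table as supplementary, and list any remaining departure in SAP Section 4.
5. For proteinuria, summarize the protein/creatinine ratio by visit and arm as Protocol 10.5.1 plans, where urine creatinine was recorded. Otherwise give the actual data limitation in Section 4.

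The cost is some programming and no new data collection. Medication is already summarized by ATC class (SAP 2.3.2), and SAP 5.5.2 already uses an ATC code to identify renal replacement therapy. The downside is that laboratory completeness is unknown, which is why the evaluable counts are needed.
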